9.5. Pharmacokinetics

Not applicable.

9.6. Pharmacodynamics

Not applicable.

9.7. Genetics

Not applicable.

9.8. Biomarkers

Not applicable.

9.9. Health Outcome/Quality of Life Measures

9.9.1. Itch Numeric Rating Scale

The Itch NRS is a patient-administered, 11 point horizontal scale anchored at 0 and 10, with 0 representing "no itch" and 10 representing "worst itch imaginable." Overall severity of a patient's itching from Ps is indicated by selecting the number that best describes the worst level of itching in the past 24 hours.

9.9.2. Fatigue Severity Numeric Rating Scale Score

The Fatigue Severity NRS is a patient-administered single-item 11-point horizontal scale anchored at 0 and 10, with 0 representing "no fatigue" and 10 representing "as bad as you can imagine." Patients rate their fatigue (weariness, tiredness) by selecting the one number that describes their worst level of fatigue during the past 24 hours.

9.9.3. Medical Outcomes Study 36-Item Short Form Health Survey Physical Component Summary and Mental Component Summary Scores

The SF-36 is a 36-item, patient-completed measure designed to be a short, multipurpose assessment of health in the areas of physical functioning, role-physical, role-emotional, bodily pain, vitality, social functioning, mental health, and general health. The 2 overarching domains of mental well-being and physical well-being are captured by the Mental Component Summary and Physical Component Summary scores, respectively. The summary scores range from 0 to 100, with higher scores indicating better levels of function and/or better health. Items are answered on Likert scales of varying lengths. The SF-36 acute version (Version 2) will be used, which has a 1 week recall period (SF-36 Health Survey Update page [WWW]).

9.9.4. European Quality of Life—5 Dimensions 5 Level [EQ-5D-5L])

The EQ-5D-5L is a standardized measure of health status used to provide a simple, generic measure of health for clinical and economic appraisal. The EQ-5D-5L consists of 2 components: a descriptive system of the respondent's health and a rating of his/her current health state using a 0- to 100-mm VAS. The descriptive system comprises the following 5 dimensions: mobility, self-care, usual activities, pain/discomfort, and anxiety/depression. Each dimension has 5 levels: no problems, slight problems, moderate problems, severe problems, and extreme problems. The respondent is asked to indicate his/her health state by selecting in the box associated with the most appropriate statement in each of the 5 dimensions. It should be noted that the numerals 1 to 5 have no arithmetic properties and should not be used as a cardinal score. The VAS records the

respondent's self-rated health on a vertical VAS, in which the endpoints are labeled "best imaginable health state" and "worst imaginable health state." This information can be used as a quantitative measure of health outcome. The EQ-5D-5L health states, defined by the EQ-5D-5L descriptive system, may be converted into a single summary index by applying a formula that essentially attaches values (also called weights) to each of the levels in each dimension (EuroQol Group [WWW]).

9.9.5. Dermatology Life Quality Index

The DLQI is a simple, patient-administered, 10 question, validated, quality-of-life questionnaire that covers 6 domains: symptoms and feelings, daily activities, leisure, work and school, personal relationships, and treatment. Response categories include "not at all," "a little," "a lot," and "very much," with corresponding scores of 0, 1, 2, and 3, respectively, and "not relevant" responses scored as "0." Totals range from 0 to 30 (less to more impairment).

9.9.6. Treatment Satisfaction Questionnaire

The Treatment Satisfaction Questionnaire is a clinician-administered questionnaire which provides an assessment of the patient's opinion of the effectiveness, safety, and overall satisfaction of the study medication. Patients will be asked to respond to questionnaire items using a 4-point Likert scale (from "very satisfied" to "very dissatisfied").

10. Statistical Considerations

10.1. Sample Size Determination

Approximately 550 patients who meet all criteria for enrollment at Visits 1 and 2 will be randomized in a 1:1 ratio at Week 0 (Visit 2) in Period 2 to ixekizumab or adalimumab (275 patients per treatment group).

Sample size was calculated assuming the proportion of patients simultaneously achieving ACR50 and PASI 100 as 13.6% and 31.3% in the adalimumab and ixekizumab treatment groups, respectively, as observed in the csDMARD-experienced population from Study RHAP. According to the nQuery software, a total sample size of 550 (with 275 per treatment group) using a 2-sided Fisher's exact test at 0.05 level of significance would yield 99% power for testing ixekizumab versus adalimumab.

This sample size would yield 78% power for testing the noninferiority of ixekizumab to adalimumab at a one-sided 0.025 level of significance based on a noninferiority margin of –12% and using ACR50 response rates of 43.8% and 44.1% as observed for the ixekizumab and adalimumab treatment groups, respectively, in the csDMARD-experienced population from Study RHAP. For testing superiority of ixekizumab to adalimumab based on PASI 100 response rates of 46.9% and 23.7% as observed for ixekizumab and adalimumab in the csDMARD-experienced population from Study RHAP, this sample size would yield 99% power using a 2-sided Fisher's exact test at 0.05 level of significance.

10.2. Populations for Analyses

For purposes of analysis, the following populations are defined:

Population	Description				
Entered	All participants who sign informed consent				
Randomized	Participants who met all entry criteria and were assigned a study treatment				
Intent-to-treat (ITT)	The ITT population consists of all randomized patients. Even if the patients do not take the assigned treatment, do not receive the correct treatment, or otherwise do not follow the protocol, they will be analyzed according to the treatment group to which they were assigned. Unless otherwise specified, efficacy and health outcomes analyses for Period 2 will be conducted on the ITT population.				
Safety	The safety population consists of all randomized patients who received at least 1 dose of study treatment in Period 2. Patients will be analyzed according to the treatment group to which they were assigned. Safety analyses for Period 2 will be conducted on this analysis set.				
Post-treatment follow-up	The post-treatment follow-up population consists of all randomized patients who received at least 1 dose of study treatment during Period 2 and have entered the Post-Treatment Follow-Up Period. Patients will be analyzed according to the treatment group to which they were assigned in Period 2. Safety analyses for Period 3 (Post-Treatment Follow-Up Period) will be conducted on this analysis set.				

10.3. Statistical Analyses

10.3.1. General Statistical Considerations

Statistical analysis of this study will be the responsibility of Lilly.

Any changes to the data analysis methods related to the primary and major secondary endpoints described in the protocol, and the justification for making the change, will be documented in the SAP and/or the clinical study report (CSR). Additional exploratory analyses of the data may be conducted as deemed appropriate.

Complete details of the planned analyses will be documented in the SAP.

10.3.1.1. General Considerations for Analyses during Period 2 (Open-Label Treatment Period)

Baseline will be defined as the last available value before the first injection of the study drug for both efficacy, health outcomes, and safety analyses. In most cases, this will be the measurement recorded at Week 0 (Visit 2).

Categorical data for baseline variables will be summarized as frequency counts and percentages. Continuous data for baseline variables will be summarized using the mean, standard deviation, minimum, maximum, median, and number of observations.

Comparisons of ixekizumab versus adalimumab will be performed for all outcome variables at all visits in Period 2; however, the primary time point of interest is Week 24.

Change from baseline at a particular visit will be calculated as the value at that visit minus the baseline value.

For outcome measures that are not collected at each post-baseline visit, data may exist at visits where the outcome measure was not scheduled to be collected, due to early discontinuation visits. In these situations, data from the early discontinuation visit that does not correspond to the planned collection schedule will be excluded from any mixed-effects models for repeated measures (MMRM) analysis. However, the data will still be used in other analyses, including shift analyses, change from baseline analyses using last observation carried forward (LOCF) imputation method, and other categorical analyses.

10.3.1.2. Missing Data Imputation

The methods for imputation of missing data to be used in this study are described below.

10.3.1.2.1. Nonresponder Imputation

Missing data for categorical efficacy and health outcome measures will be imputed using the nonresponder imputation (NRI) method. Patients will be considered nonresponders if they do not meet the clinical response criteria or have missing clinical response data at the time point of analysis. Randomized patients without at least one post-baseline observation will also be defined as nonresponders for the NRI analysis.

10.3.1.2.2. Last Observation Carried Forward

Missing data for continuous efficacy and health outcomes variables will be imputed using LOCF method. For patients discontinuing investigational product or having missing data at a visit, the last nonmissing post-baseline observation before discontinuation or before the visit with missing data will be carried forward to the corresponding time point. Randomized patients without at least one post-baseline observation will not be included in LOCF analyses.

In addition to NRI and LOCF, other imputation methods may be used as deemed appropriate.

10.3.1.3. Adjustment for Multiple Comparisons

A multiple testing strategy for the primary and major secondary endpoints will be implemented to control the family-wise type I error rate at a 2-sided α level of 0.05. The primary and major secondary endpoints will be sequentially tested in the following order to compare ixekizumab vs adalimumab, using the primary analysis method.

- 1. Test 1 for Primary Endpoint Proportion of patients simultaneously achieving ACR50 and PASI 100 at Week 24: A superiority test of the primary endpoint will be performed at an overall 2-sided $\alpha = 0.05$ using the methods described in Section 10.3.3.1.1.
- 2. Test 2 for Major Secondary Endpoint #1 Proportion of patients achieving ACR50 at Week 24: If the test for the primary endpoint is significant, then a noninferiority test for the major secondary endpoint #1 will be performed using the methods described in Section 10.3.3.3.
- 3. Test 3 for Major Secondary Endpoint #2 Proportion of patients achieving PASI 100 at Week 24: If the test for major secondary endpoint #1 is significant, then a superiority test for major secondary endpoint #2 will be performed using the methods described in Section 10.3.3.1.1.

If a test in this sequence is not significant, all subsequent tests will be considered nonsignificant.

There will be no adjustment for multiple comparisons for any other analyses.

10.3.2. Treatment Group Comparability

10.3.2.1. Patient Disposition

A detailed description of patient disposition will be provided at the end of the study. All patients who discontinue from the study treatment and the study will be identified, and the extent of their participation in the study will be reported. Patient disposition will be summarized and will include reasons for discontinuation. The reasons for discontinuation during Period 2 will be tested between treatment groups using Fisher's exact test.

10.3.2.2. Patient Characteristics

Baseline characteristics, clinical, and health outcome measurements will be summarized for the ITT population. Baseline characteristics will include sex, age, age category, weight, BMI, race, geographic region, baseline disease severity, duration of disease, previous nonbiologic systemic therapy, and previous biologic therapy. Baseline clinical measurements will include ACR component scores, PASI total score, DAS28-CRP, CRP, Modified CPDAI, HAQ-DI, Itch NRS score, NAPSI Fingernails, SPARCC Enthesitis Index, LEI, LDI-B, and other QoL scores.

Treatment group comparisons between ixekizumab and adalimumab will be conducted using Fisher's exact test for categorical data and an analysis of variance model with treatment as a factor for continuous data.

10.3.2.3. Concomitant Therapy

Previous and concomitant medications (including concomitant topical products such as emollients and other nonprescription topical products) will be summarized for patients who enter each treatment period and will be presented by World Health Organization Anatomic Therapeutic Class (WHOATC) Level 1 and generic name. Treatment group comparisons between ixekizumab and adalimumab in Period 2 will be conducted using Fisher's exact test.

10.3.2.4. Treatment Compliance

Treatment compliance with investigational product will be summarized for patients who enter Period 2. A patient will be considered compliant overall to ixekizumab or adalimumab if he/she is missing no more than 20% of the expected doses, does not miss 2 consecutive doses, and does not double-dose (that is, take more injections at the same time point than specified in the protocol). Proportions of patients compliant by visit and overall will be compared between treatment groups during Period 2 using Fisher's exact test.

10.3.3. Efficacy Analyses

10.3.3.1. Primary Analysis Method

10.3.3.1.1. Categorical Variables

Unless specified otherwise, the primary analysis method for the categorical efficacy and health outcome variables will be using a logistic regression model with treatment, concomitant csDMARD use at baseline (Yes vs No), and moderate-to-severe plaque psoriasis involvement (Yes vs No) as factors and NRI method. Treatment group comparisons will be made at all visits up to Week 52 and odds ratios and their corresponding 95% confidence intervals (CIs) will be reported.

10.3.3.1.2. Continuous Variables

Unless specified otherwise, the primary analysis method for all continuous efficacy and health outcome variables will be using a MMRM analysis. The model will include treatment group, concomitant csDMARD use (Yes vs No) at baseline, moderate-to-severe plaque psoriasis involvement (Yes vs No), baseline value, visit, baseline-by-visit interaction, and treatment-by-visit interaction as fixed factors. The covariance structure to model the within-patient errors will be unstructured. If the unstructured covariance matrix results in a lack of convergence, the heterogeneous Toeplitz covariance structure, followed by the heterogeneous autoregressive covariance structure will be used. The Kenward-Roger method will be used to estimate the denominator degrees of freedom. Type III tests for the least squares means will be used for the statistical comparison; the 95% CI will also be reported. Treatment group comparisons at all visits up to Week 52 will be made.

10.3.3.2. Secondary Analysis Method

10.3.3.2.1. Categorical Variables

Secondary analyses for treatment comparisons on the categorical efficacy variables will be conducted using a Fisher's exact test.

10.3.3.2.2. Continuous Variables

Secondary analyses for treatment comparisons on continuous outcome variables will be performed using an analysis of covariance (ANCOVA) model and LOCF imputation method. The details of the analysis model will be presented in the SAP.

10.3.3.3. Methodology for Noninferiority Test

For assessing noninferiority of ixekizumab to adalimumab, missing data will be imputed using the NRI method. Noninferiority analysis will be performed on the ITT population using a prespecified fixed margin approach. There is no universally accepted value for what is considered to be a clinically unimportant difference between 2 treatments for a particular efficacy measure. We will consider the points from EMEA Committee for Medicinal Products for Human Use (CHMP) (CHMP 2005) and FDA guidance (2016) which state that an appropriate noninferiority margin should be based on both clinical and statistical grounds.

The null hypothesis will be rejected if the lower bound of the 2-sided 95% CI for the difference in proportions of responders on ixekizumab minus adalimumab is greater than the prespecified margin, meaning ixekizumab will be deemed noninferior to adalimumab. If the lower bound of the CI exceeds 0 (the corresponding p-value will also be produced), then ixekizumab will be deemed superior to adalimumab. The 95% CIs for the difference in proportions will be calculated using the simple asymptotic method, without continuity correction (that is, normal approximation to the binomial distribution).

Based on EMEA CHMP (CHMP 2005), FDA guidance (2016), and Weinblatt et al. (2013), a noninferiority margin of –12.0% for ACR50 between ixekizumab and adalimumab (ie, response rate of ixekizumab – response rate of adalimumab) is considered appropriate. This noninferiority margin represents an approximately 50% preservation of the adalimumab treatment effect (based on the difference between adalimumab and placebo) observed in a historical Phase 3 study for adalimumab 40 mg twice weekly compared with placebo (Mease et al 2005) and Study RHAP.

If it is deemed appropriate to perform noninferiority tests on endpoints other than ACR50, the details about selection of noninferiority margins for the other endpoints will be presented in the SAP.

10.3.4. Safety Analyses

Safety will be assessed by summarizing and analyzing AEs, laboratory analytes including neutrophil counts, vital signs, and concomitant medications. The duration of exposure will also be summarized.

The primary safety analyses will focus on comparisons of ixekizumab versus adalimumab in Period 2. Fisher's exact test will be used for all AEs and other categorical safety data. Continuous vital sign and laboratory values will be analyzed using ANCOVA method with

treatment and baseline value in the model. Other continuous safety variables will be analyzed by t-tests, unless otherwise stated.

Summaries of safety data collected during the Post-Treatment Follow-Up Period (Period 3) will be presented separately. Unless otherwise specified, the follow-up baseline is defined as the last nonmissing assessment on or prior to the Week 52 (Visit 11) or early discontinuation visit.

The categorical safety measures will be summarized with incidence rates. The mean change of the continuous safety measures will be summarized by visits.

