5.2. Number of Participants

Approximately 917 participants will be screened (assuming a 40% screen failure rate) to achieve randomization of 550 participants (275 per treatment group) and approximately 396 patients are expected to complete Week 52 (assuming 72% completion rate at Week 52).

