10.3.7. Interim Analyses

An interim database lock will occur, and the analysis will be performed at the time (that is, a cutoff date) when the last patient completes Visit 8 (Week 24), completes ETV, or discontinues from Period 2. This database lock will include all data collected by the cutoff date including data after Week 24 from the Open-Label Treatment Period (Period 2) and follow-up data from patients who have begun Post-Treatment Follow-Up Period (Period 3).

This interim database lock at Week 24 will be considered the primary database lock for this study because all primary and major secondary study objectives will be assessed at this time. Since the primary time point of interest is Week 24, efficacy and health outcomes data will be

reported up to Week 24 because of the lack of complete data for all patients beyond this visit. However, all safety data collected up to the cutoff date will be reported.

A final database lock will occur after all enrolled patients have completed or discontinued the Post-Treatment Follow-Up Period (Period 3). After the final database lock, all efficacy, health outcomes, and safety data collected until study completion will be reported.

There will be no data monitoring committee.

11. References

- Amjevita [package insert]. Thousand Oaks, CA: Amgen Inc; 2016.
- Antoni C, Krueger GG, de Vlam K, Birbara C, Beutler A, Guzzo C, Zhou B, Dooley LT, Kavanaugh A. IMPACT 2 Investigators. Infliximab improves signs and symptoms of psoriatic arthritis: results of the IMPACT 2 trial. *Ann Rheum Dis.* 2005a;64(8):1150–1157.
- Antoni CE, Kavanaugh A, Kirkham B Tutuncu Z, Burmester GR, Schneider U, Furst DE, Molitor J, Keystone E, Gladman D, Manger B, Wassenberg S, Weier R, Wallace DJ, Weisman MH, Kalden JR, Smolen J. Sustained benefits of infliximab therapy for dermatologic and articular manifestations of psoriatic arthritis: results from the Infliximab Multinational Psoriatic Arthritis Controlled Trial (IMPACT). *Arthritis Rheum*. 2005b;52(4):1227-1236.

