Data collected at early termination visits will be mapped to the next planned visit number for that patient. For by-visit summaries, only visits in which a measure was scheduled to be collected will be summarized. Unplanned/unscheduled measurements will be excluded from the mixed-effects model of repeated measures (MMRM) analysis. However, the data will still be used in other analyses; such analyses include, but are not limited to, shift analyses and modified baseline observation carried forward (mBOCF) endpoint analyses.

All confidence intervals (CIs) and statistical tests will be 2-sided with an α level of 0.05 unless specified otherwise. P-values that are greater than or equal to 0.001, and less than or equal to 0.999, will be presented to 3 decimal places. All other p-values that are less than 0.001 will be presented as <0.001, while p-values greater than 0.999 will be presented as >0.999. Confidence intervals will be presented to 1 more decimal place than the raw data.

Age, sex, and race will be reported on all by-patient listings unless otherwise specified. Sex will be abbreviated as follows: female (F) and male (M). Race will be abbreviated as follows: American Indian or Alaska Native (AI), Asian (AS), Black or African American (BL), Native Hawaiian or other Pacific Islander (NH), White (WH), and Multiple (MU).

Table RHCF.6.1 gives the treatment groups to be displayed for each treatment period and analysis population. Analysis populations are defined in Section 6.1.3. Note: “IXE” and “ADA” will be included in treatment group names for ixekizumab and adalimumab, respectively, in the statistical reports where applicable.

Table RHCF.6.1. Treatment Groups for Each Treatment Period and Analysis Population

Treatment Period	Analysis Population	Treatment Groups	Abbreviation	Comparison
Open-Label Treatment Period (Period 2)	Intent-to-Treat Population; Safety Population	Ixekizumab 80 mg Q4W (or Q2W/Q4W) Adalimumab 40 mg Q2W	IXE ADA	IXE vs ADA
Post-Treatment Follow-up Period (Period 3) ^a	Follow-up Population	Ixekizumab 80 mg Q4W (or Q2W/Q4W) Adalimumab 40 mg Q2W	IXE ADA	Not applicable

Abbreviations = ADA = adalimumab; IXE = ixekizumab; Q2W = every 2 weeks; Q4W = every 4 weeks.

^a Treatment group refers to the dosage regimen that the patient received immediately prior to entering the Post-Treatment Follow-up Period.

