6.15.1. Extent of Exposure

Duration of exposure to study drug will be summarized by treatment group using descriptive statistics; the summary will also include the total exposure in patient years, mean, and median total dose. Exposure of safety population in the Open-Label Treatment Period (Period 2) will be summarized.

The duration of exposure will be calculated as follows:

- *Duration of exposure (days) =*
Date of last visit (scheduled or unscheduled) during the treatment period –
Date of first injection for the treatment period + 1

- Total exposure in patient years will be calculated as follows:

$$\text{Total exposure in patient years} = \frac{\text{Sum of duration (days) of exposures for all patients in treatment group}}{365.25}$$

- Total dose (in mg) is calculated by the summation of dose for each active injection taken during the treatment period.
- Note that the total number of injections received will be calculated using the response to the question “Was the injection given?” on the *Study administration* electronic eCRF page.

Descriptive statistics will be provided for patient days of exposure and the frequency of patients falling into the following different exposure ranges (that is, only the exposure ranges that fall within the treatment period will be presented) will be summarized:

- >0, ≥7 days, ≥14 days, ≥30 days, ≥60 days, ≥90 days, ≥120 days, ≥183 days, ≥365 days.
- >0 to <7 days, ≥7 to <14 days, ≥14 to <30 days, ≥30 to <60 days, ≥60 to <90 days, ≥90 to <120 days, ≥120 to <183 days, ≥183 to <365 days, and ≥365 days.

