 - If year, month, and day are missing, then use the patient's last visit date in the follow-up period.
 - If either month or month and day are missing, then use December 31.
 - If only day is missing, then use the last day of the month.
 - The imputed date will not be beyond the patient's last visit date in the follow-up period.
- For the end time:
 - Impute as 23:59.
- If there is any doubt, the event will be flagged as treatment-emergent or follow-up emergent according to the corresponding study period. If a follow-up emergent event was already counted as treatment-emergent during the prior treatment period, it will not be counted as a follow-up emergent event.

An overview table will be provided and will include the frequency and percentage of patients who experienced a TEAE, TEAE by maximum severity, a treatment-emergent adverse events of special interest (AESI), serious adverse event (SAE), death, or discontinued from the study due to an AE (including death) will be summarized by treatment group for the Open-Label Treatment Period.

In general, for all AE-related summaries, the number and percentage of patients experiencing the events will be presented by dosing regimen. When the SOC is presented, events will be ordered by decreasing frequency in the ixekizumab treatment group within SOC. When the SOC is not presented, the events will be ordered by decreasing frequency in the ixekizumab treatment group. For incidence counts, each patient will be counted only once within each PT and within each SOC. Percentages will be based on the number of patients in a particular treatment group. For events that are gender specific, the denominator and computation of the percentage will include only patients from the given gender.

The following summary tables will be provided for the Open-Label Treatment Period (Safety Population):

- An overview summary of AEs
- TEAEs, by SOC and PT
- TEAEs, by PT
- TEAEs by maximum severity, by SOC and PT

The following summary tables will be provided for the Post-Treatment Follow-Up Period (Follow-Up Population):

- FEAEs, by maximum severity, by SOC and PT

By-patient listing of all TEAEs will be provided.

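### Period 2 harms are compared as crude percentages with no exposure-adjusted or time-to-first-event summary, so the comparison is distorted if dropout unrelated to the event differs by arm

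*Protocol*

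**What the plan says.** - **Test.** Protocol 10.3.4 states that "Fisher's exact test will be used for all AEs and other categorical safety data", and SAP 6.15 repeats this. SAP 6.1 adds that "statistical tests will be 2-sided with an α level of 0.05 unless specified otherwise".
- **Summary measure.** Under SAP 6.15.2.1, "the number and percentage of patients experiencing the events will be presented by dosing regimen", with patients in the arm as the denominator. SAP 6.15.3 and Table RHCF.6.7 plan no rate per patient-year. Where incidence rates are mentioned, SAP 6.1.2 and 6.15 tie them to Period 3.
- **Counting window.** A TEAE must start or worsen by the last treatment-period visit (Protocol 10.3.4.1, SAP 6.15.2.1). A patient who stops early has an early termination visit and enters Period 3. Later events are follow-up emergent, and Table RHCF.6.1 plans no treatment comparison for that period.
- **Exposure.** SAP 6.15.1 describes duration of exposure, and "the summary will also include the total exposure in patient years, mean, and median total dose".
- **Time-based harm analysis.** SAP 6.8 plans Kaplan-Meier summaries of time to discontinuation for any reason and due to an adverse event, and a log-rank test on time to discontinuation. Table RHCF.6.7 also plans durations of some infections, but these measure how long an event lasts, not time to onset.
- **Dropout.** Protocol 5.2: "approximately 396 patients are expected to complete Week 52", "assuming 72% completion rate at Week 52". No split by arm is given.
- **Week 24 lock.** Protocol 10.3.7 reports efficacy up to Week 24, then adds: "However, all safety data collected up to the cutoff date will be reported".

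**The concern.** A patient who leaves early stays in the denominator of a crude percentage but stops contributing time in which a TEAE can be counted. If the arms lose patients at different rates for reasons unrelated to the event, equal hazards produce unequal percentages.

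A difference is plausible, though not stated. Treatment is open-label. Patients who need another effective psoriatic arthritis or psoriasis agent must stop (Protocol 8.1.1). The sample size assumes primary response rates of 31.3% and 13.6%. Dropout for lack of efficacy could therefore differ by arm. Safety is part of the stated purpose of the trial, and a real excess could be understated or an apparent one created.

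The second issue is what the Week 24 lock percentages mean. Patients still on treatment at the cutoff will have between 24 and 52 weeks of safety follow-up, so the percentage describes no fixed period. It can be set neither beside the Week 24 efficacy results nor beside the final safety tables.

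**Working it through.** **The plan's own figure.** 550 × 0.72 = 396 completers, as Protocol 5.2 states. That is 28% stopping by Week 52, overall.

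**Inputs.** From the documents: 275 per arm and a two-sided Fisher test at 0.05. Assumed, because the documents give no values: event rates, the dropout split (kept to a mean of 28%), constant hazards, dropout independent of the event, and accrual length.

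**Formulas.** Let F be the 52-week event risk without dropout and d the dropout by Week 52. With time in years:
- event hazard λ = −ln(1 − F); dropout hazard γ = −ln(1 − d)
- crude proportion = λ/(λ + γ) × [1 − exp(−(λ + γ))]
- mean time at risk = [1 − exp(−(λ + γ))]/(λ + γ)

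**Worked case, F = 40%, equal hazards (λ = 0.5108).**
- d = 20%: γ = 0.2231; 0.5108/0.7340 × (1 − exp(−0.7340)) = 0.6960 × 0.5200 = 36.2%
- d = 36%: γ = 0.4463; 0.5108/0.9571 × (1 − exp(−0.9571)) = 0.5337 × 0.6160 = 32.9%
- crude ratio = 0.91, although the true ratio is 1.00

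The first-event rates recover the truth. The arms expect 99.5 patients with an event in 194.8 patient-years at risk and 90.4 in 177.0. Both give 51.1 per 100 patient-years.

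**Range (equal true hazards).** The last column is the exact probability, at 275 per arm, that Fisher's test declares the higher-dropout arm safer; its nominal maximum is 2.5%.

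| Dropout | Crude, F = 10% | Crude, F = 40% | Crude ratio, F = 5% to 85% | Wrong call, F = 40% |
|---|---|---|---|---|
| 28% / 28% | 8.5% / 8.5% | 34.6% / 34.6% | 1.00 | 2.0% |
| 24% / 32% | 8.8% / 8.3% | 35.4% / 33.7% | 0.95–0.96 | 5.1% |
| 20% / 36% | 9.0% / 8.1% | 36.2% / 32.9% | 0.90–0.93 | 11.0% |

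**A real excess.** Take a true hazard ratio of 1.25 against the higher-dropout arm, with F = 40% in the other arm. The crude ratio is 1.18 with 28% dropout in both arms and 1.08 at 20%/36%.

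**Dropout that follows the event.** With the same hazard ratio, 20% dropout in one arm and about 35% in the other because some patients stop after the event, the crude result is 36.2% against 42.8%. The event is counted before the patient leaves, so the arm that loses more patients does not look safer.

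**Week 24 lock.** Take F = 40% and 28% dropout in both arms. The crude percentage is 19.5% over a fixed 24 weeks and 34.6% over 52 weeks. At the lock it is 27.1%, 30.8% or 32.1% for 26, 52 or 78 weeks of uniform accrual. The between-arm ratio is 1.00 in every case. The lock changes the meaning of the percentage, not the comparison.

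**Limit of the rate.** Suppose all risk falls in the first 8 weeks and is equal in both arms (10% or 40%), with 20%/36% dropout. The crude ratio is then about 0.98, but the rate ratio is about 1.09, a false excess in the arm with more dropout.

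**The case against.** The strongest case against has five parts.

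- **There is a time-based analysis, and dropout is examined.** SAP 6.8 plans Kaplan-Meier for discontinuation due to an adverse event, and Fisher tests on discontinuation overall and by reason. This stands: it would be wrong to say that harms are handled only as crude percentages, and a dropout imbalance would be visible. But it covers one outcome, and nothing carries an imbalance into the TEAE, SAE or AESI comparisons.
- **No imbalance is documented.** This stands. A reader might infer from the 28% that the comparison is already biased. That figure is overall, and equal dropout with equal hazards gives a ratio of exactly 1.00.
- **The less well tolerated arm need not look safer.** This stands. A reader might infer that whichever arm loses more patients gains in the tables. That holds for dropout unrelated to the event, not for dropout that the event causes.
- **Safety p-values are descriptive.** SAP 6.15 says so, and no confirmatory claim rests on them. This lowers the stakes, but the percentages themselves would be distorted.
- **Other documents may hold more.** SAP 6.15.3.1 lets a program safety plan supersede it on special safety topics, and SAP 6.1 places further safety analyses in a separate document. Neither is available here. The two documents under review nowhere say that an adjusted estimate exists.

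The early-onset example also stands: rates per patient-year are not a neutral replacement and should only supplement the percentages.

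**Conclusion.** The point holds as a conditional one. Period 2 TEAEs, SAEs and AESIs have no planned summary that accounts for time at risk, although patient-years are already derived. If dropout unrelated to the event differs by arm, the crude risk ratio under equal hazards moves from 1.00 to about 0.95–0.96 at 24%/32% and about 0.90–0.93 at 20%/36%. These figures rest on assumed splits, constant hazards and independent dropout.

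The Week 24 lock is a separate matter of interpretation. A reader might infer that unequal follow-up there favours one arm. The documents do not support this: the spread comes from staggered entry, which randomization balances.

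This is an inexpensive improvement to the safety reporting. It does not touch the primary or major secondary efficacy tests.

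**What to change.** In SAP 6.15.2.1, 6.15.3 and Table RHCF.6.7, keep the numbers, percentages and Fisher's tests, and add:

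1. At both locks, for any TEAE, SAEs, adverse events leading to discontinuation and each AESI: patients with a first event per 100 patient-years at risk, censored at first event or last treatment-period visit, with a rate ratio and 95% CI.
2. For SAEs and AESIs: cumulative incidence over time to first event, by arm, because a rate per patient-year assumes a constant hazard and can mislead for early-onset events.
3. At the Week 24 lock: incidence restricted to Weeks 0–24, so that safety and efficacy refer to the same period.
4. A note with the rates stating the constant-hazard assumption.

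The cost is more safety output and some programming. Event, dosing and visit dates are already collected, so no new data are needed.
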